#### 6.1.1 Screening Visit

- Informed consent
- Demographics
  - Medical history
- Concomitant Medications
- Physical exam
- Vital signs and weight
- ECOG performance status (Appendix A: ECOG Performance Status Criteria)
- Urine or Serum Pregnancy Test
- PT/INR and aPTT
- Complete Blood Count (CBC) with differential
- Serum chemistry
- Urinalysis
- T3, FT4 and TSH
- ECG
- Tumor Imaging CT preferred
- Tumor Biopsy/Archival biopsy (for PD-L1 status)
- Correlative Blood Collection

# 6.1.2 Treatment Phase

Pembrolizumab infusions will be administered every 3 weeks  $\pm$  3 days until disease progression or patient is withdrawn for another reason. OBP-301 is to be administered prior to pembrolizumab in this patient population. All patients will receive OBP-301 at 2 x10^12 viral particles/ tumor injection administered every two weeks x 4 injection encounters. The tumor will be injected with OBP-301 four times (day 1, day 15, day 29, day 43). However, there may be some exceptions for OBP-301 injections which are outlined below.

- A. Up to 1 additional tumor injection encounter may be considered in discussion with the PI ([name]), which may be given 2 weeks after the 4th injection of OBP-301.
- B. Patients who initially respond to combination therapy may be rechallenged with OBP-301 at the time of disease progression, after discussion with the principal investigator.

Criteria for the additional single dose of OBP-301 is that the patient has not had disease progression and has had no grade 3 or 4 events related to OBP-301.

# 6.1.3 Follow up Phase

Patients with disease progression will be followed every 3 months for survival for up to 96 weeks from study start. This assessment can occur by telephone or some other remote monitoring.

# 6.1.4 Patient Withdrawal Criteria

In accordance with applicable regulations, a participant has the right to withdraw from the study, at any time and for any reason, without prejudice to his future medical care.

Withdrawal from the study and therapeutic measures taken shall be at the discretion of the Investigator. A full explanation for the discontinuation from the study should be made in the participant's medical records and in the eCRF.

Premature discontinuation from active study participation may occur at any time due to any of the following reasons:

- Any situation where, in the opinion of the Investigator or the Medical Monitor, continued participation in the study would not be in the best interest of the patient.
- Positive pregnancy test
- Patient initiates other anti-cancer therapy. The anti-cancer therapy will be documented in the medical record and eCRF.
- Progressive neoplastic disease, unless the Investigator feels this may be pseudoprogression, in which case the patient may remain on study until the next evaluation for extent of disease.
- An intercurrent illness or AE that requires concomitant medication that precludes further study participation
- Patient is unable or unwilling to comply with study procedures.
- Patient is lost to follow-up.
- Patient withdraws consent.
- Termination of the study by the Sponsor.
- Request by a Health Authority.

In addition, the Sponsor will discontinue a patient from active study treatment for any of the following criteria (subjects will continue to be followed as apprioprate for outcomes and toxicities:

- Patients who experience a Grade 4 hematologic toxicity or a Grade 3 or greater nonhematologic toxicity attributable to OBP-301 or the endoscopic procedure that has not resolved to Grade 1 (or basline) within 2 weeks of onset.
- OBP-301 injection will be delayed for any ongoing Grade 2 toxicity at the time of the next scheduled injection after consultation with the Principal Investigator. Patients who require a delay of OBP-301 injection of > 4 weeks (i.e., approximately 6 weeks from the previous injection) due to lack of resolution to Grade 1 toxicity will be discontinued from the study after consultation with Medical Monitor and Principal Investigator.

After apparent disease progression (PD) is observed, administration of OBP-301 may be continued as per iRECIST. Immune-related disease progression (irPD) will be confirmed if the increase in tumor burden is  $\geq 25\%$  relative to nadir (minimum recorded tumor burden). The confirmation is completed by a repeat, consecutive assessment no less than 4 weeks from the date the disease progression was first documented. If in the opinion of the investigator, the disease progression is not clinically significant, then the patient may continue to receive OBP-301 treatment.

The reason(s) for premature study discontinuation/withdrawal will be documented along with the date of withdrawal. AEs should be documented according to the study calendar.

For all patients who discontinue, a Final Visit will be performed within  $28 \pm 5$  days after the last IP administration (see study calendar). If a participant is withdrawn because of an AE, the Investigator must arrange for the participant to have appropriate follow-up care until the AE is

resolved or has stabilized. Unresolved AEs will be followed until the last scheduled follow-up visit or until the Investigator and Medical Monitor determine that further follow-up is no longer indicated. Investigators should attempt to collect the survival information as dictated by the Schedule of Events in the Study calendar.

Patients who discontinue the active study participation will not be replaced.

Any enrolled patients who are discontinued before study dosing will be documented as screen failures in the eCRF and replaced. No follow-up is required for these patients.

## 6.2 Informed Consent Form

Each patient is required to provide informed consent before participating in the study.

Before performance of any study procedures, potential patients will attend a screening session at which time they will be provided with full information concerning details of the study assessments and procedures. They will also be provided with the ICF. Before being asked to sign the ICF, patients will be given time to review the study information and ask any questions. A copy of the signed ICF must be provided to the patient.

## 6.3 Demographic Data and Baseline Characteristics

Gender, date of birth, height, and weight, as well as race and ethnic origin will be recorded for each patient and age and body mass index calculated from these data.

## 6.4 Medical History, Concomitant Disease, Previous and Ongoing Medications

A detailed medical history, including surgical and cancer history, will be recorded and will include any conditions reported by the patient or noted by the Investigator in each body system. Medical history is defined as any condition that started and ended before the Screening Visit. A concomitant disease is defined as any condition detected at the Screening Visit that started after ICF signature or was started before the Screening Visit and is still ongoing at the Screening Visit.

Prior medication taken before the Screening Visit and any concomitant medication will be documented. Prior medication is defined as any medication taken within 4 weeks of screening visit. Concomitant medications are those medications which the patient is currently taking at any particular visit.

Records should include the drug name (preferably both generic and trade name), route of administration (e.g., oral, intravenous), injection and frequency (expressed in metric units, for example, mg, mL, or IU), indication, and the start and, if applicable, the stop date (day, month, and year). Therapy changes (including changes of regimen) during the study have to be documented. All concomitant medications will be recorded in the eCRF.

#### 6.5 Safety Assessments

#### 6.5.1 Adverse Events

Definitions, management of, and special considerations for AEs are provided in Section 7. Adverse events will be collected at each contact with the patient. Questions regarding the presence of adverse events should be open-ended without leading the patient.

# 6.5.2 Physical Examination

The physical examination is to be conducted by the Investigator or designated fully trained representative. Performance status will also be determined at screening as well as at each subsequent visit as oulined in the section study schedule. Patients will be graded according to the ECOG Performance Status Scale.

Performance Status	Definition
0	Fully active, able to carry on all pre-disease performance without restriction.
1	Restricted in physically strenuous activity but ambulatory and able to carry out work of a light or sedentary nature, e.g., light housework, office work.
2	Ambulatory and capable of self-care but unable to carry out any work activities; up and about more than 50% of waking hours.
3	Capable of limited self-care, confined to bed or chair more than 50% of waking hours.
4	Completely disabled; cannot carry on any self-care; totally confined to bed or chair.

# 6.5.3 Vital Signs

Vital signs will include measurements of heart rate, systolic and diastolic blood pressures while the patient is in a seated position, and temperature.

#### 6.5.4 Electrocardiogram

During screening of patients, a standard baseline 12-lead ECG will be recorded after the patient has rested for 5 minutes. The Investigator or designee will review all ECGs. The following parameters will be documented: rhythm, heart rate, PR interval, QRS interval, QT interval, and QTc. Every ECG must be assessed as normal, abnormal – clinically not significant, or abnormal – clinically significant. A diagnosis must be provided in the eCRF for all ECGs assessed as abnormal – clinically significant. If clinically indicated, additional ECGs may be obtained during the study.

# 6.5.5 Laboratory Assessments

# 6.5.5.1 Clinical Chemistry, Hematology, Coagulation Parameters, and Urine Analysis for Safety Panel

Following table illustrates laboratory assessments, which will be performed at prescribed intervals as per schedule of events.

Page 53 V8.0

Hematology	Coagulation	Serum Chemistry	Urine Analysis

 
Hemoglobin
 
Hematocrit
 
Red blood cell count
 
White blood cell (WBC) count
 
Platelet count
 
WBC differentials
 
	
 
International normalized ratio
 
Prothrombin time
 
	
 
Sodium
 
Potassium
 
Chloride
 
Bicarbonate
 
Blood urea nitrogen
 
Creatinine
 
Glucose
 
Alanine transaminase
 
Aspartate transaminase
 
Aspartate transaminase
 
Alkaline phosphatase
 
Lactate dehydrogenase
 
Bilirubin (total and direct)
 
Total protein
 
Albumin
 
Calcium
 
Magnesium
 
Phosphorous
 
	
 
pH
 
Specific gravity
 
Glucose
 
Ketones
 
Bilirubin
 
Hemoglobin
 
Protein
 
Microsopic if any dipstick value 2+ or greater
 

Table 4Clinical Laboratory Parameters for Safety Panel

#### 6.5.5.2 Pregnancy Testing and Post-Menopausal Status

A serum or urine pregnancy test will be performed on all women of childbearing potential at Screening.

The post-menopause is defined as the time after which a woman has experienced 12 consecutive months of amenorrhea (lack of menstruation) without a period. If a woman claims she is post-menopausal, but has had her menses within 12 months, a follicle stimulating hormone (FSH) test must be performed and must be within acceptable limits of the post-menopausal status. If the post-menopausal status of a female is confirmed, the pregnancy tests will not be performed.

All pregnancies detected during the study must be reported and handled as described in Section 7.2.

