	
 
treatment, with the exception of prostate cancer controlled with androgen deprivation therapy.
 
7. Has received a live vaccine within 30 days of planned start of study therapy.
 
8. Patients known to have acute or chronic active hepatitis B virus (HBV), hepatitis C virus (HCV), or human immunodeficiency virus (HIV).
 
9. Has any evidence of active, non-infectious pneumonitis or interstitial lung disease requiring steroids.
 
10. Has an active infection requiring systemic therapy within 2 weeks of Day 1.
 
11. Has known psychiatric or substance abuse disorders that would interfere with cooperation with the requirements of the trial.
 
12. Is pregnant or breastfeeding, or expecting to conceive or father children within the projected duration of the trial, starting with the screening visit through 120 days after the last dose of trial treatment.
 
13. Previous severe hypersensitivity to another monoclonal antibody
 
14. Has a history or current evidence of any condition, therapy, or laboratory abnormality that might confound the results of the trial, interfere with the subject's participation for the full duration of the trial, or is not in the best interest of the subject to participate, in the opinion of the treating investigator.
 
15. Uncontrolled intercurrent illness including, but not limited to, uncontrolled diabetes, ongoing or active infection, symptomatic congestive heart failure, unstable angina pectoris, cardiac arrhythmia, or psychiatric illness/psychological incompetence, whereby in the opinion of the Investigator the patient is assessed as being unable to provide information, consent, or comply with the
 

	16. Patients who are pregnant or breastfeeding, or expecting to conceive or father children within the projected timeframe of the study, starting from the time of the Screening Visit through 4 months (120 days) after the last OBP-301 administration. Females of childbearing potential must have a negative serum or urine pregnancy test at Screening. A female not of childbearing potential is one who has undergone bilateral oophorectomy or who has had no menses for 12 consecutive months.
Study Procedures:	1. OBP-301 $2x10^{12}$ VP / tumor injection every 2 weeks x four injections.
	* Up to one additional injection may be considered in discussion with the PI ([name]).
	2. Pembrolizumab 200 mg intravenous every 3 weeks
Study Endpoints:	Primary Endpoint:

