# **4 STUDY POPULATION**

### 4.1 Selection of Study Population

Only those patients will be included in the study that meet inclusion and exclusion criteria as outlined below.

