#### 4.2 Inclusion Criteria

Patients who meet all of the following criteria will be considered for inclusion in the study:

- 1. Be willing and able to provide written informed consent for the trial.
- 2. Be  $\geq 18$  years of age on the day of signing the informed consent.
- 3. Have an Eastern Cooperative Oncology Group (ECOG) performance status of 0-2.
- 4. Have histologically or cytologically confirmed advanced or metastatic gastroesophageal adenocarcinoma amenable to intratumoral injection (i.e. at least 1 cm in size).
- 5. Tumor must be PD-L1 positive, as defined by a combined positive score (CPS).
- 6. Patient must have received at least 2 lines of systemic therapy for advanced disease
- 7. Have one or more measurable lesions based on RECIST v1.1.
- 8. Be willing to provide tissue; newly obtained biopsy specimens or formalin-fixed, paraffinembedded (FFPE) block specimens.
- 9. Female subjects of childbearing potential have a negative urine or serum pregnancy test within 7 days prior to enrollment. If the urine test is positive or cannot be confirmed as negative, a serum pregnancy test will be required. It is allowed that the test at the same day at 7 days prior to enrollment. And male / female subjects of childbearing potential must agree to use an adequate method of contraception starting with signing the informed consent through 120 days after the last dose of study medication.
- 10. Demonstrated adequate organ function as defined in following criteria. All screening labs should be performed within 14 days of enrollment. Note: Subject must not have taken transfusion, hematopoietic agent; granulocyte-colony stimulating factor (G-CSF) etc., and/or oxygen supplementation within 7 days before the screening labs.
- a. Absolute neutrophil count (ANC)  $\geq$  1,000 /mm3
- b. Platelets  $\geq 100,000 / \text{mm3}$
- c. Hemoglobin  $\geq 8.0 \text{ g/dL}$
- d. Serum total bilirubin  $\leq 2.0 \text{ mg/dL}$
- e. Aspartate aminotransferase (AST) (SGOT) and alanine aminotransferase (ALT) (SGPT) $\leq 3x$  Upper limit of normal (ULN). For subjects with liver metastases  $\leq 5x$  ULN.
- f. Serum creatinine $\leq 2.0 \text{ mg/dL}$ ; or if serum creatinine > 2.0 mg/dL, measured or calculated creatinine/clearance  $\geq$ 45 mL/min (Cockcroft-Gault formula).
- 11. Life expectancy of  $\geq 4$  months from the first OBP-301 treatment.

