- 15. Uncontrolled intercurrent illness including, but not limited to, uncontrolled diabetes, ongoing or active infection, symptomatic congestive heart failure, unstable angina pectoris, cardiac arrhythmia, or psychiatric illness/psychological incompetence, whereby in the opinion of the Investigator the patient is assessed as being unable to provide information, consent, or comply with the study requirements and procedures.
- 16. Patients who are pregnant or breastfeeding, or expecting to conceive or father children within the projected timeframe of the study, starting from the time of the Screening Visit through 4 months (120 days) after the last OBP-301 administration. Females of childbearing potential must have a negative serum or urine pregnancy test at screening. A female not of childbearing

Page 31 V8.0 potential is one who has undergone bilateral oophorectomy or who has had no menses for 12 consecutive months.

Page 32 V8.0

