#### 4.4.2 Patient Registration – Part 2 (All Sites)

Study participants will be centrally registered Monday through Friday from 9:00am to 4:00pm with the Weill Cornell Medicine Joint Clinical Trials Office (JCTO). To register a new study subject, email the following documents to [contact]:

- Completed WCM subject registration form
- First and last page of the fully executed informed consent form, plus additional pages if checkboxes for correlative studies are required
- Fully executed HIPAA research authorization form
- Eligibility checklist signed and dated by investigator and research nurse
- Documentation of any eligibility waivers granted
- Redacted source documentation to verify eligibility

Note that attachments larger than 4.5 MB are not accepted, so larger attachments should be split into more than one email. Central registration information is reviewed and entered into the REDCap database.

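### Section 6.5.5.2 lets an FSH result waive the pregnancy test in a woman who menstruated within 12 months, although exclusion 16 and the section's own 12-month definition point to testing her

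*Combined protocol and SAP*

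**What the plan says.** Section 6.5.5.2 takes four steps. It orders a serum or urine test at screening for all women of childbearing potential. It defines post-menopause as 12 months in a row without menstruation. It then turns to the woman who claims to be post-menopausal "but has had her menses within 12 months, a follicle stimulating hormone (FSH) test must be performed", and requires the FSH result to fall in the post-menopausal range. It ends: "If the post-menopausal status of a female is confirmed, the pregnancy tests will not be performed".

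Exclusion 16 gives the only definition of childbearing potential, identically in the Synopsis and in Section 4.3: "A female not of childbearing potential is one who has undergone bilateral oophorectomy or who has had no menses for 12 consecutive months". For everyone else the rule in Section 4.3 is: "Females of childbearing potential must have a negative serum or urine pregnancy test at screening".

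Inclusion 9 in Section 4.2 adds a time window: "Female subjects of childbearing potential have a negative urine or serum pregnancy test within 7 days prior to enrollment". It does not define the term.

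The Schedule of Events (Section 6.1, with footnote m) and the screening list (Section 6.1.1) both show the pregnancy test, at screening only, without an FSH exemption.

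**The concern.** The protocol gives two answers for one woman. A site that follows the last sentence of Section 6.5.5.2 omits a test that exclusion 16 requires. A site that follows exclusion 16 performs a test that Section 6.5.5.2 says is not done. Either way the site departs from a written instruction.

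The pregnancy test is scheduled once, so no later scheduled test would catch an omission. The protocol also treats exposure in pregnancy as a hazard: its safety guidelines keep pregnant women away from treated patients' body fluids and from preparing or giving OBP-301.

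**Working it through.** The plan states no figure on this point, so the main check applies each rule to one case: a woman with intact ovaries who says she is post-menopausal, menstruated within the past 12 months, and has FSH in the post-menopausal range.

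- **Section 6.5.5.2, FSH sentence and waiver.** FSH is required and is in range. No other confirmation step is described. Status is confirmed, so there is no pregnancy test.
- **Section 6.5.5.2, opening sentence and definition.** She has not gone 12 months without menses, so she does not meet the section's own definition of post-menopause. Read with exclusion 16, the opening sentence has her tested.
- **Exclusion 16.** She has neither bilateral oophorectomy nor 12 months without menses. She is of childbearing potential, and a negative test is required.
- **Inclusion 9.** The same result, but only through exclusion 16's definition. It is not a second, independent conflict.
- **Schedule of Events and Section 6.1.1.** The test is listed with no FSH exemption, and FSH itself is not listed. FSH is also absent from the safety laboratory table in Section 6.5.5.1.

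The waiver therefore disagrees with exclusion 16, with the schedule, and with the definition in its own section.

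**How many women.** The documents give none of the shares below; all are assumptions.

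- Patients: 41 planned over both stages (Synopsis and Section 8.8). If the trial stops after stage 1, the same 10% allowance for unevaluable patients gives 18 / 0.9 = 20.
- Share of women: 25% to 35%.
- Of these, menses in the past year and no oophorectomy: 5% to 15%.
- Of these, claiming menopause and having FSH in range: 25% to 75%.

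Women untested if every other check failed = patients × the three shares.

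- Both stages, low: 41 × 0.25 × 0.05 × 0.25 = 0.128
- Both stages, high: 41 × 0.35 × 0.15 × 0.75 = 1.614
- Stage 1 only, low: 20 × 0.25 × 0.05 × 0.25 = 0.0625
- Stage 1 only, high: 20 × 0.35 × 0.15 × 0.75 = 0.7875

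These are women among all patients enrolled. At 25% to 35%, the 41 patients would include about 10 to 14 women (41 × 0.25 = 10.25; 41 × 0.35 = 14.35).

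**How many pregnancies missed.** If 0.1% to 1% of the untested women were pregnant (also assumed), the expected number over both stages runs from 0.128 × 0.001 = 0.00013 to 1.614 × 0.01 = 0.016.

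**The case against.** The best defence is that the status to be confirmed is the one the section has just defined, namely 12 months without menses. The text makes FSH necessary for this woman but never says that it is sufficient. On that reading a recently menstruating woman can never be confirmed, and she is tested. The section's opening sentence supports this, as does the instruction at the start of Section 6 to follow the Schedule of Events, which has the pregnancy test and no FSH slot.

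Part of this stands. That FSH alone is enough is an inference from the text, and much of the protocol already points toward testing. But the defence leaves the FSH step without a purpose: FSH is ordered only for women who fail the 12-month definition, and it is the only confirmation step described. The natural reading is that an in-range result confirms status and removes the test. Nothing expressly overrides that instruction.

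The second defence is that other checks would catch the omission. Section 4.1 says: "Only those patients will be included in the study that meet inclusion and exclusion criteria as outlined below". Section 4.4.2 requires a signed eligibility checklist and "Redacted source documentation to verify eligibility", and adds: "Central registration information is reviewed and entered into the REDCap database". The pre-injection list in Section 5.2.3 confirms eligibility again. This stands as a reason to call the point minor. It does not remove the conflict, because those who make these checks work from a protocol that contains both rules.

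A reader might go further and infer that the protocol admits pregnant women, or that exposed pregnancies should be expected. The documents do not support that. Exclusions 12 and 16 bar pregnant patients whether or not a test was done, and an untested woman is not a pregnant one.

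**Conclusion.** The inconsistency is real and minor. On its natural reading, Section 6.5.5.2 waives the pregnancy test for a woman whom exclusion 16 requires to be tested. This is more than missing detail, because a stated rule would omit a required test.

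The number affected is probably no more than one or two women among 41 patients, and possibly none. That range rests wholly on assumed shares, and it also supposes that Section 4.1, the checklist, the central review and the pre-injection check all give way to Section 6.5.5.2. The expected number of missed pregnancies is far below one at every value tried. The response-rate analysis, the two-stage boundaries and the error rates are untouched.

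**What to change.** Amend the last part of Section 6.5.5.2 so that the pregnancy test is omitted only for women with bilateral oophorectomy or no menses for 12 consecutive months. State that every other woman is tested at screening whatever her FSH result.

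The cost is one paragraph of wording at the next amendment and one extra urine or serum test in a rare patient. The test is already a screening procedure, so sites need nothing new.

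Adding an FSH route to exclusion 16 would also remove the conflict. It would still waive the test in a woman who menstruated within the year, so the first option is the safer one. Choosing between them is a clinical judgement that the documents do not settle.
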